9.7.5 Safety Analyses

Safety analyses will be performed separately for Cohort A and B, and will include all enrolled patients with an actual follow-up. Statistical analysis and reporting of AEs will be descriptive in nature, will be based on BI standards, and will focus on adverse drug reactions (ADRs) to Pradaxa[®] and VKA. No hypothesis testing is planned.

Occurrences of ADRs will be analyzed relative to the number of patients treated as well as observed person-years (i.e. time at risk). Safety analysis will be based on the concept of treatment emergent ADRs. Patients will be analyzed according to the anticoagulation treatment received at the time of the event. If no concurrent anticoagulation treatment is administered, then events occurring within a washout period of 3 days (for Pradaxa[®]) or 6 days (for VKA) after discontinuation of anticoagulation treatment will be assigned to the last treatment given. This washout period will also be included as time at risk for derivation of total person-years. ADRs that deteriorate under treatment will also be considered as “treatment emergent”. Events occurring prior to first intake of anticoagulation treatment prescribed at baseline, during periods without any anticoagulation treatment (excluding washout periods), or after the end of the 6 month follow-up (excluding washout periods) will not be considered treatment emergent events and will not be included in the summary tables.

The following parameters will be included in the safety analyses:

- Adverse drug reactions
- Adverse drug reactions leading to discontinuation of anticoagulation treatment
- Serious adverse drug reactions
- Adverse events leading to deaths

Schedule of Planned Analyses

No interim analysis is planned for Cohort A.

For Cohort B, it is planned that an interim analysis that assesses the comparability of patients in the Pradaxa[®] and VKA groups based on propensity scores will be performed when approximately half of the target sample size is reached (see details in Section 9.7.2.1).

For each cohort, the final analyses as specified in Section 9.7.2 will be performed once the data collection is completed, the data sets are cleaned, and the database is locked for that cohort. The final analysis for both cohorts may be performed together, if their complete data becomes available at the same time. One final report will be prepared at the completion of both cohorts.

Additional reports (e.g. for country-specific analyses) may be prepared if deemed appropriate and will be specified in the SEAP.

9.7.6 Handling Of Missing Data

Every reasonable attempt will be undertaken to ensure completeness of data collection. Imputation will be permitted, if deemed appropriate and on a case-by-case basis, depending on the extent and distribution of missing values, and will be described in the SEAP.

The percentage of and reason for loss to follow-up will be summarized overall in Cohort A, by treatment in Cohort B, and by other relevant factors. In addition, if the proportion of

patients with loss to follow-up is substantial enough (e.g. $\geq 10\%$) to warrant further investigation, baseline characteristics will be described for patients who were lost to follow-up in comparison to patients who have completed follow-up.

9.8 QUALITY CONTROL

The following processes will be implemented to ensure data completeness and data quality:

Data Edit Checks:

The electronic CRF (eCRF) will include programmable edit checks to obtain feedback if data is missing, out of range, illogical or potentially erroneous.

These checks will be performed once data is entered into the eCRF. Thus the data entered in to the eCRF will be validated within the system and the physician will receive alerts for missing or inconsistent data. In case any changes of already entered data will be required, an audit trail will be available.

Medical monitoring:

A review of applicable entered eCRF data will be performed to verify patient eligibility to ensure that the analysed patient population corresponds to the protocol-described population. In addition eCRFs/completed patient related questionnaires will also be reviewed for verification that no non reported safety event is present.

Source data verification:

No regular source data verification is planned in this non-interventional study. However, in case of issues (i.e. high amount of missing data, data discrepancies, protocol violations, etcetera) detected at a site with the measures described above, a for-cause onsite visit can be planned to perform a sample check of source data.

9.9 LIMITATIONS OF THE RESEARCH METHODS

Consecutive enrolment will be employed to ensure that specific types of patients are not selected by site staff to participate.

VKA has been the mainstay of SPAF for many years. It is widely available, affordable but does require regular INR monitoring. Pradaxa[®] is more expensive, may or may not be reimbursed but doesn't require the continual INR monitoring. There are a number of different types of bias that could influence the data collection and analysis from these cohorts such as selection bias, information bias and channelling bias.

The study is designed to collect new data. The entry criteria are non-restrictive which will permit the enrolment of a broad patient population. The choice of treatment is at the discretion of the investigator. Therefore the data collected in this study should reflect the real world treatment patterns and patient characteristics.

Selection bias:

Selection bias could occur at both the site (physician) level and the patient level. If sites where Pradaxa[®] is used frequently differ systematically with respect to patient or the routine procedures from sites that use Pradaxa[®] less frequently, the between site difference could lead to non-comparability between the patients. To minimize the site level selection bias, the goal is to have participating centres that have access to all available treatment options for SPAF that are approved for use in that country.

Selection bias at the patient level could occur if sites preferentially enrol specific patients into the study. To minimize selection bias at the patient level, consecutive enrolment is performed.

- **Information / observer bias:**

Information or observer bias may occur when information is collected differently between

two groups. E.g. if the observer/physician has more knowledge about the use of VKA treatment, the patients exposure to VKA treatment or the disease status and development as compared to Pradaxa[®]. Also, a VKA patient will be more often seen. Such information may result in differences in the way information is collected, measured or interpreted by the investigator in each of the treatment groups (cohort A or B (B1, B2)). The use of a standardized protocol and eCRF for data collection, but also the use of standardized questionnaires (PACT-Q) which have to be completed by the patients themselves, will minimize the information/observer bias.

- **Loss to follow-up:**

All efforts will be made to minimize loss to follow-up in patients who are enrolled. Patients who are lost to follow-up will be characterized and compared to the remaining patients and the reason and time point of lost to follow-up will be evaluated.

Channelling bias:

Channelling bias can occur due to preferential prescribing in relation to different risks for events of interest e.g. if Pradaxa[®] is prescribed more frequently to high risk patients than to other treatments, a high rate of outcome events could be expected in the Pradaxa[®] group. In order to control for potential channelling, an assessment will be conducted to monitor the comparability of important patient baseline characteristics. Propensity score matching is planned to account for potential differences.

Recall bias:

Recall bias refers to the phenomenon when the outcomes of treatment (either good or bad) may colour the patient's recollection of events prior to or during the treatment. To minimize recall bias, patient reported outcomes will be assessed using validated questionnaires within a limited period of time to minimize recall bias.

Confounding:

Statistical techniques, such as adjustment for covariates and propensity score matching will be used to correct for identified confounders. However unidentified confounders cannot be controlled for using statistical analysis. The employed methods are described in the data analysis section.

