2. LIST OF ABBREVIATIONS

AE	Adverse Event
AESI	Adverse Event of Special interest
ADR	Adverse Drug Reaction
AF	Atrial Fibrillation
ANCOVA	Analysis of Covariance
BI	Boehringer Ingelheim
CA	Competent Authority
CHA ₂ DS ₂ - VASc score	Congestive heart failure, Hypertension, Age (≥ 75), Diabetes mellitus, Stroke/TIA, Vascular disease, Age 65-74, Sex category
CI	Confidence Interval
CML	Local Clinical Monitor
CRA	Clinical Research Associate
CRF	Case Report Form
CTP	Clinical Trial Protocol
DEDP	Drug Exposure During Pregnancy
DMP	Data Management Plan
DVT	Deep Venous Thrombosis
eCRF	Electronic Case Report Form
EC	Ethics Committee
ECG	Electrocardiogram
EDC	Electronic Data Capture
EMA	European Medicine Agency
EudraCT	European Clinical Trials Database
FDA	Food and Drug Administration
GCP	Good Clinical Practice
GEP	Good Epidemiological Practice
GPP	Good Pharmacoepidemiology Practice
GVP	Good Pharmacovigilance Practices
GPV CTC	Global Pharmacovigilance Clinical Trial Coordinator
HAS-BLED	Hypertension, Abnormal renal and liver function, Stroke (1 point), Bleeding history or predisposition, Labile INR, Elderly (>65 years), Drugs and Alcohol.
ICH	International Conference of Harmonisation
ICSR	Individual Case Safety Report
IEC	Independent Ethics Committee
INR	International Normalized Ratio
IRB	Institutional Review Board
ISF	Investigator Site File
MAH	Marketing Authorisation Holder Activities
n.a.	Not applicable / not available
NIS	Non-Interventional Study
NVAF	Non valvular atrial fibrillation
OPU	Operative Unit
OAC	Oral Anticoagulation
PACT-Q [®]	Perception of Anticoagulant Treatment Questionnaire

PE	Pulmonary Embolism
SAE	Serious Adverse Event
SDV	Source Data Verification
SEAP	Statistical and Epidemiological Analysis Plan
SEASK	South East Asia South Korea
SOP	Standard Operating Procedure
SPAF	Stroke Prophylaxis (or Prevention) in Atrial Fibrillation
TMF	Trial Master File
VKA	Vitamin K Antagonist

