9.7 DATA ANALYSIS

9.7.1 Study Design

In this non-interventional study, cross-sectional data at study baseline and longitudinal follow-up data over 6 months will be collected for non-valvular AF patients with a current VKA therapy and subsequent initiation of Pradaxa[®] in Cohort A, and for newly diagnosed AF patients initiated on Pradaxa[®] or VKA in Cohort B.

Baseline data will be analyzed using a descriptive approach. Data from the longitudinal follow-up will be summarized descriptively. For Cohort A, mean differences in PACT-Q2 scores between assessments will be assessed using paired t-tests. For Cohort B, mean differences in PACT-Q2 scores between Pradaxa[®] and VKA patients will be assessed using propensity score matched analysis.

Due to the nature of this non-interventional study, there is no (confirmatory) hypothesis testing foreseen in a strict statistical sense. Analyses are descriptive in nature and confidence intervals and p-values from statistical models are used for exploratory purposes.

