9.7.3 Main analysis

Patient demographics and disease characteristics at baseline as described in section 9.3.2 will be summarized descriptively for all eligible patients in Cohort A and by treatment in Cohort B. This analysis may be repeated by additional relevant factors (e.g. country) that will be specified in the SEAP.

For Cohort A, the mean PACT-Q2 scores at the second and last assessments will be compared with the baseline assessment using paired t-tests.

For Cohort B, mean PACT-Q2 scores will be compared between Pradaxa[®] and VKA patients at the second and last assessments. Given the nature of this non-interventional study, patient in the two treatment groups may differ with regard to important baseline demographics and disease characteristics. When approximately half of the target sample size is reached, propensity scores that estimate the probabilities that patients would be initiated on Pradaxa[®] will be calculated using a logistic regression model including relevant baseline factors. The percentage of Pradaxa[®] and VKA patients that are matched with a 1:1 ratio and without replacement based on propensity scores will be calculated to assess the comparability of the two patient populations, and to estimate the loss of patients from the comparative analysis. Details of the propensity score model and the matching procedure, such as the choice of algorithm and caliper width will be described in the SEAP. If a sufficient percentage of matching (e.g. 90%) is achieved, the loss is considered minimal. If the percentage is considered not to be sufficient, the target sample size might be raised to increase the power of the comparative analysis.

For the final comparative analysis for Cohort B, Pradaxa[®] and VKA patients will be matched based on propensity scores following the same approach as described above. To assess the performance of the propensity score matching procedure, patient demographics and disease characteristics at baseline will be descriptively summarized again for the matched patients by treatment. Finally, the mean PACT-Q2 scores at each of the second and last assessments will be compared between the matched Pradaxa[®] and VKA patients using a paired t-test.

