7.5 METHODS ADDRESSING CONFOUNDING/EFFECT MEASURE MODIFICATION

Propensity score matching will be used to correct for identified confounders. However unidentified confounders cannot be controlled for using statistical analysis. For details on the propensity score matching method, see Section 7.6.

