 - Variable selection will be performed with caution to avoid the inclusion of highly correlated variables as well as over-parameterization.
 - All covariates from the list above will be set as required covariates in the propensity score model to ensure balance of baseline characteristics of patients. If any additional covariates are deemed necessary to be included in the propensity score model, they need to be defined before database lock.

Pradaxa[®] and VKA patients will then be matched based on propensity scores using a variable ratio, parallel, balanced 1:n, nearest neighbour matching algorithm with a caliper width of 0.05 and without replacement. The publicly available SAS macro provided by Rassen et al. (5) will be used.

Finally, the percentage of Pradaxa[®] and VKA patients that are matched with an appropriate maximum ratio (e.g. 2:1) according to the actual patient distribution will be calculated to assess the comparability of the two patient populations, and to estimate the loss of patients from the comparative analysis.

For the final comparative analysis for Cohort B, Pradaxa[®] and VKA patients will be matched based on propensity scores following the same approach as described above. To assess the performance of the propensity score matching procedure, patient demographics and disease characteristics at baseline will be descriptively summarized again for the matched patients by treatment. For each matched set that includes multiple Pradaxa patients, the mean PACT-Q2 score will be calculated for the Pradaxa patients and used in the final comparative analysis. Finally, the mean PACT-Q2 scores at each of the second and last assessments will be compared between the matched Pradaxa[®] and VKA patients using paired t-tests.

For both cohorts, the primary analyses will be based on the actual anticoagulation treatment the patients receive (i.e. “as treated” analysis). A patient is considered to have permanently discontinued initial anticoagulation treatment if other relevant anticoagulation treatment is initiated or otherwise dependent on the duration of treatment interruption. Whether a patient discontinued from the Pradaxa[®] or VKA is recorded on the eCRF. Patients who have permanently discontinued initial anticoagulation treatment at the time of an assessment will be excluded from all analyses where data from that assessment is included.

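### Cohort B's matched comparison has no covariate adjustment and no planned response to imbalance left after matching, although Protocol 9.9 names adjustment as a method

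*Protocol*

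**What the plan says.** Protocol 9.9, under confounding, gives the general statement: "Statistical techniques, such as adjustment for covariates and propensity score matching will be used to correct for identified confounders". The same paragraph then defers: "The employed methods are described in the data analysis section".

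That data analysis section is narrower. In Protocol 9.7.1, differences between Pradaxa and VKA "patients will be assessed using propensity score matched analysis". Protocol 9.7.3 ends: "Finally, the mean PACT-Q2 scores at each of the second and last assessments will be compared between the matched" groups, by paired t-test. The protocol's abbreviation list defines ANCOVA ("Analysis of Covariance"), but the supplied text uses it nowhere.

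SAP 7.5 carries the 9.9 sentence in a shorter form: "Propensity score matching will be used to correct for identified confounders". SAP 7.6 lists 14 baseline covariates, all required in the propensity model, and matches with a caliper of 0.05 without replacement. Where a set has several Pradaxa patients, their scores are averaged. The section ends: "the mean PACT-Q2 scores at each of the second and last assessments will be compared between the matched" Pradaxa and VKA "patients using paired t-tests". Baseline characteristics are tabulated again after matching, with no balance metric, threshold or consequence.

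**The concern.** Matching on a propensity score balances covariates on average. It does not make the two members of a set alike on each covariate. Three features of SAP 7.6 make some leftover difference plausible: age, renal function and the risk scores are banded coarsely, six countries become two categories, and the caliper's scale is not stated.

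A second source arises after matching. Patients who have discontinued are excluded at each assessment, certain PACT-Q scores are excluded, and Protocol 9.2.2.3 arranges no visits solely for the study. If sets are formed once and then lose a member, the sets left at Visit 2 or Visit 3 need not be balanced, least of all if scores go missing for different kinds of patient in the two arms.

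With no covariate in the outcome comparison and no rule tied to the balance table, any such difference on a prognostic covariate goes into the main Cohort B estimate. The covariates needed to deal with it are already in the analysis data.

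**Working it through.** **1. The plan's own figure.** Protocol 9.5 gives N = 1192, 30% loss to follow-up and matching, two-sided alpha 0.05 and a standardized difference of 0.14. Pairs = 1192 × 0.70 / 2 = 417. Power = Φ(0.14 × √417 − 1.96) = Φ(2.859 − 1.96) = 81.6%. The stated power of over 80% is reproduced in the paired form without any adjustment.

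**2. Where covariates act.**

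| Place | Matching | Covariates in the outcome comparison |
|---|---|---|
| Protocol 9.9 | named | named, as an example |
| Protocol 9.7.1 and 9.7.3 | yes | none |
| SAP 7.5 | yes | none |
| SAP 7.6 | yes | none (propensity model only) |

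**3. What imbalance does to the estimate.** The paired estimate is the mean of the within-set differences. For one covariate with correlation r to the score and residual standardized mean difference (SMD) δ, the shift is r × δ × SD. The SD of 16 is from Protocol 9.5; r and δ are assumed.

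| Residual SMD | r = 0.1 | r = 0.2 | r = 0.3 |
|---|---|---|---|
| 0.05 | 0.08 | 0.16 | 0.24 |
| 0.10 | 0.16 | 0.32 | 0.48 |
| 0.20 | 0.32 | 0.64 | 0.96 |

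Values are in points. The target is 0.14 × 16 = 2.24 points, so 0.48 points is 21% of it. Because the power holds in the paired form, 0.14 may instead be in units of the pair-difference SD. With uncorrelated pairs that SD is 16 × √2 = 22.6, the target is 3.17 points, and the share is 15%.

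**4. Idealized precision.** If covariates explain a share R² of the score variance, the CI shortens by 1 − √(1 − R²): 2.5%, 5% and 11% at R² = 0.05, 0.10 and 0.20. The documents give no R², so these values are illustrations only.

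**5. Simulations (all settings assumed: 14 binary covariates, 1:1 nearest-neighbour matching, caliper 0.05 on the probability scale).**

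- *Adjusted pair differences, 834 patients, no loss after matching.* The largest SMD averaged 0.06 to 0.08. Bias was at most about 0.15 points unadjusted, and similar adjusted. The reported SE changed by about +2%, 0% and −4% to −5% at R² = 0.05, 0.10 and 0.20. The true SD of the estimator did not improve (ratio 1.00 to 1.07).
- *Regression in the matched sample with SEs clustered on set, 1192 patients, about 17% of scores missing.* The largest SMD rose from about 0.056 after matching to 0.10 when sets were lost at random, and to 0.15 when missingness differed by arm. With random loss the reported SE fell by about 3%, 5% and 9%. The true SD fell by 1% to 2% at the two lower R² values and by 6% at 0.20. With arm-differential missingness the unadjusted bias was 0.26, 0.29 and 0.46 points, and the adjusted bias at most about 0.1.
- *The same estimator with missingness depending on arm and covariate.* Adjustment removed about 0.8 to 1.5 points of bias. The true SD fell by only 0% to 4%.

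**The case against.** A reader might infer that the SAP silently withdrew a protocol commitment. The documents do not support that. The list in 9.9 is introduced by words that make it illustrative, it stands in a limitations section, and it points to the data analysis section for the methods used. That section never contained an adjusted outcome model. The looseness is inside the protocol, and the SAP follows 9.7.3. What stands is that 9.9 and SAP 7.5 now read differently and that neither SAP section 4.1 nor its history table mentions it.

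A reader might also infer that measured confounders are ignored. They are not. All listed covariates are required in the propensity model, comparability is assessed at about half enrolment, and further covariates may be added before database lock. None of these steps says what follows if balance after matching is poor.

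A third inference would be that precision is clearly being wasted. Cohort B has no baseline PACT-Q2, probably the strongest predictor, and the simulated gain ran from nothing to modest depending on the estimator. Clustering on site as well could widen the interval.

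Three further objections have force. The SAP does not say whether matching precedes the visit-level exclusions, so the broken-set mechanism is conditional. A paired t-test suits the matched design, and p-values are exploratory. An outcome regression adds model dependence. These argue for keeping the t-test in the report, not against adding an adjusted analysis.

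**Conclusion.** The point holds as a low-cost improvement. It is not an error in a stated figure: the power is met without adjustment. Protocol 9.9 and the operative sections need to agree, and the Cohort B estimate has no planned protection against imbalance that matching leaves or that loss of scores creates.

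The benefit is mainly protection against bias. With little or no loss after matching it is close to nil. It becomes material, from roughly a quarter of a point to 1.5 points in the settings tried, if scores go missing differently by arm in ways related to the covariates. Protocol 9.5 cites registry differences of −0.6 and 1.1 points, although the study is by design not powered for effects that small. Any precision gain is small and conditional. The 0.48-point shift and the 2.5%, 5% and 11% CI figures rest on assumed correlation, SMD and R² values. Residual imbalance is a risk without a planned remedy, not a shown result. Adjustment would not deal with unmeasured confounding, or with missingness that depends on the score itself.

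**What to change.** Reconcile Protocol 9.9 with 9.7.3 and SAP 7.5 and 7.6 by pre-specifying, for each PACT-Q2 dimension at each of Visits 2 and 3:

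- A linear regression in the matched sample on treatment plus the propensity covariates, with SEs clustered on matched set. Weight each of the n Pradaxa patients in a set by 1/n and the VKA patient by 1. With treatment alone in the model, these weights return the mean set difference behind the paired t-test, so the two results are directly comparable.
- Reporting beside the paired t-test, either as the main analysis or at minimum as a sensitivity analysis, with the choice stated in advance.
- Standardized differences for every propensity covariate in the sets actually analysed at that visit, with a stated threshold and the consequence of exceeding it.
- The order of matching and visit-level exclusions.

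The cost is SAP wording, one extra model per score and visit, and some model dependence. No new data are needed. Making the regression the main analysis would also change the test named in Protocol 9.7.3; adding it as a sensitivity analysis would not.
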